8.2.2.2. Other Organs

Liver Enzymes

Liver enzymes is assessed by AST (U/L), ALT (U/L), GGT (U/L), LDH (U/L) and bilirubin ($\mu\text{mol/L}$) at Baseline, Day 1, Day 3, Day 5, Day 7, Day 14, Day 21 and Day 28.

The observed values and change from baseline for liver enzymes will be calculated by visit and summarized by descriptive statistics.

Time-course plots similar to the plot being produced for the primary endpoint will be presented for mean AST, ALT and LDH displaying the optimal recAP and placebo groups only.

All liver enzymes data will be listed.

Lung Function

Lung function is assessed, for patients on mechanical ventilation, by PaO₂, P/F ratio, PEEP (cmH₂O) and tidal volume (mL/kg) daily from Day 1 to Day 28. The observed values and change from baseline for PaO₂, P/F ratio, PEEP and tidal volume will be calculated by visit and summarized with descriptive statistics. For non-mechanical ventilation liters of administered oxygen will be assessed.

Table 8-2 Normal Ranges for Lung Function Parameters

Parameter	Normal Range
PCO ₂	4.7 – 6.4 kPa or 35-48 mmHg
PO ₂	10.0 – 13.3 kPa or 75 – 100 mmHg
Oxygen saturation	95 – 100%

The following conversion rate will be performed for PO₂ and PCO₂ where needed
 kilopascal (kPa) x 7.5 = mmHg

All lung function data will be listed.

Mechanical Ventilation from Day 1 to Day 28

A ventilator-free day is defined as a day on which a patient was not on ventilator (invasive or non-invasive mechanical ventilation). The start and stop dates of the patient been under mechanical ventilation is collected in the eCRF, therefore days not on ventilator correspond to days that are outside of the start and stop dates of when the patient is on mechanical ventilation. If the method of mechanical ventilation is changed with no interruption, it corresponds to the same episode of mechanical ventilation.

Should a patient die or withdraw prior to Day 28, the days remaining in this period will be counted as per the status of the patient at time of death or withdrawal.

Ventilator-free days are calculated as 28 days minus the number of days a patient is on ventilator during this period. Descriptive statistics will be presented for the number of ventilator-free days.

Time to being off ventilator from Day 1 to Day 28, for those patients that are on ventilator at Day 1, will be compared between treatment groups by displaying Kaplan-Meier plots. Time to being off ventilator is calculated as:

$$\text{Date of being off ventilator} - \text{Start date of study drug infusion} + 1.$$

For patients that have been off ventilator and had to be put back on ventilator the latest case of ventilation will be used to calculate time to being off ventilator. Patients that do not have an off ventilator date will be censored at the earliest of Day 28 or date of study withdrawal. Patients not on ventilator at the start of study drug infusion will be excluded from this analysis.

A table of the corresponding Kaplan-Meier estimates will be presented displaying the number of patients at risk, number of patients censored, number of patients off-ventilator,

cumulative number of patients off-ventilator, Kaplan-Meier estimate, and standard errors of the Kaplan-Meier estimates. Summary statistics (based on the Kaplan-Meier analysis) for the time to being off ventilator will also be included in a separate table.

Exploratory analysis of time to being off-ventilator will be undertaken for the comparison of the optimal recAP dose and placebo using a log rank test stratified by site. The hazard ratio, associated 95% confidence interval and p-value from the comparisons of the optimal recAP dose versus Placebo will be presented.

The number and percentage of patients not on mechanical ventilation at baseline, requiring and not requiring mechanical ventilation during the first 28 days will also be presented.

Mechanical and non-mechanical ventilation data will be listed.

Shock-free from Day 1 to Day 28

Shock-free is defined as a patient that is not on vasopressors or inotropic agents. Shock-free days and Time to being shock-free will be analyzed in an identical fashion to the method described above.

Shock-free data will be listed.

SOFA

The SOFA questionnaire assesses 6 systems organs: respiratory system, central nervous system, cardiovascular hypotension, liver, coagulation and renal system. Each system has 5 response options ranging from 0 to 4 that reflect increasing levels of failure. Any response > 0 is classed as a dysfunctional organ.

The SOFA score is assessed at baseline, and at all planned visits from Day 1 to Day 28 (as long as the patient is in the ICU/Intermediate care) and at discharge from ICU/Intermediate care. The observed values and change from baseline for total SOFA score and respiratory system, central nervous system, cardiovascular hypotension, liver, coagulation and renal system individually will be calculated by visit and summarized with descriptive statistics.

A time-course plot similar to the plot being produced for the primary endpoint will be presented for the mean SOFA score displaying the optimal recAP and placebo groups only.

The number of dysfunctional organs for each patient will be summarized with counts and percentages by visit.

All SOFA data will be listed.

Deaths during the 90 day study period

Mortality at Day 28 and Day 90 will be summarized by the counts and percentages of patients who died prior to or at these timepoints. Exploratory analysis will also be undertaken to compare the number of deaths between the optimal recAP dose and placebo at Day 28 and Day 90 using a Cochran-Mantel-Haenzel (CMH) test. The CMH test statistic and the corresponding p-value will be presented.

Should either of the CMH tests at Day 28 and Day 90 produce a significant result, time to death from Day 1 to Day 90 will be compared between treatment groups by displaying Kaplan-Meier plots. Time to death is calculated as:

$$\text{Date of death} - \text{Start date of study drug infusion} + 1.$$

Patients that do not die will be censored at the earliest of Day 90 or date of study withdrawal. A table of the corresponding Kaplan-Meier estimates will be presented displaying the number of patients at risk, number of patients censored, number of deaths, cumulative number of deaths, Kaplan-Meier estimate, and standard errors of the Kaplan-Meier estimates. Summary statistics (based on the Kaplan-Meier analysis) for the time to death will also be included in a separate table.

Purine Data

Purine data will be listed along with urine volume and urine sample collection start date and collection times for the Iohexol set.

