### 7.3.2 Other Organs

Endpoints for organs other than renal function include the following:

- Liver enzymes (AST, ALT, GGT, LDH, bilirubin but excluding AP).
- Lung function as assessed by arterial PaO2, FiO2, P/F ratio, PEEP, and tidal volume in mechanically ventilated patients.
- Ventilator-free days (from Day 1 to Day 28, inclusive), i.e., 28 days minus the number of days a patient is on ventilator during this period. Should a patient die or withdraw prior to Day 28, the days remaining in this period will be counted as per the status of the patient at time of death or withdrawal.
- Time from start of first administration of study drug to being off-ventilator (from Day 1 to Day 28, inclusive) for those patients who are on ventilator at the start of this period. Patients who remain on ventilator will be censored at the earliest of Day 28 or withdrawal from the study for any reason.
- Shock-free days (during the period Day 1 to Day 28, inclusive), i.e., 28 days minus the number of days a patient is on inotropic or vasopressor therapy during this period. Should a patient die or withdraw prior to Day 28, the days remaining in this period will be counted as per the status of the patient at time of death or withdrawal. A patient is considered to be shock free if he or she is not on vasopressors or inotropic agents (including but not limited to noradrenaline, adrenaline, dobutamine, dopamine, vasopressin, and enoximone).
- Time from start of first administration of treatment to being shock free (from Day 1 to Day 28, inclusive) for those patients who are not shock free at the start of this period. Patients who do not become shock free will be censored at the earliest of Day 28 or withdrawal from the study for any reason.
- SOFA scores during ICU or intermediate care unit stay.
- Number of dysfunctional organs as assessed by SOFA scores.
- Deaths during the 90-day study period (by recording date).

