5.1. Disposition

Patient disposition will be summarized for the all Enrolled Set. A disposition of patients includes the number and percentage of patients for the following categories: patients who were not randomly assigned to treatment, patients in the ITT Combined Set, patients treated (Safety Set), patients in the PP Day 1-7 Combined Set, patients in the PP Day 1-7 Part 1 Analysis Set, patients in the ITT Part 1 Set, patients in the ITT Part 1 Interim Set, patients in the ITT Part 2 Set, patients in the PP Day 1-7 Part 2 Set, patients in the PK Set and patients in the Iohexol Set. The number and percentage of patients who completed the study and patients who discontinued from the study will be summarized for the ITT Combined Set, the ITT Part 1 Set, ITT Part 1 Interim Set and the ITT Part 2 Set. The percentages will be based on the number of patients in each analysis set.

The reasons for study discontinuation will also be summarized in this table. The reason for study discontinuation includes the following: Adverse Event, Lab abnormality, Patient Withdrew consent, Investigator Decision, Sponsor termination of study, Protocol Non-Compliance or violation, Death and Other. The percentages will be based on the number of patients who discontinued from the study.

The disposition table will be repeated by site for the all Enrolled Set.

Patient disposition data will be presented in a listing.

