The observed values and change from baseline in visual analog scale will be calculated by visit and summarized with descriptive statistics.

All EQ-5D data will be listed.

Discharge from ICU/Intermediate care for Day 1 to Day 28 and Day 1 to Day 90

Total time in ICU/Intermediate care is calculated as the number of days a patient has been in the ICU/Intermediate care from the start of first study drug infusion to discharge where discharge is defined as the time of actual transfer (up to Day 28 and Day 90) and will be summarized by the descriptive statistics. For the calculation of Total time in ICU/Immediate care for Day 1 to 28 if a subject discontinued or died prior to Day 28 whilst still in ICU, the ICU discharge date is assumed as Day 28. For the calculation of Total time in ICU/Immediate care for Day 1 to 90, if a subject discontinued or died whilst still in ICU, then the discharge date will be assumed as taking the maximum of Day 28 or study discontinuation date.

Time to being discharged from ICU/Intermediate care will be compared between treatment groups by displaying Kaplan-Meier plots, where discharge is defined as the time when the decision was made to transfer the patient (as opposed to the time of actual transfer). Time to being discharged from ICU/Intermediate care is calculated as:

Planned discharge date from ICU/Intermediate care – Start date of study drug infusion + 1.

For patients that have been discharged from the ICU/Intermediate care and had to be readmitted, only their first case of admission will be used to calculate time to being discharged from the ICU/Intermediate care. Patients that have transferred to another ICU/Intermediate care will not be classed as discharged from the ICU/Intermediate care. Patients that have not been discharged from the ICU/Intermediate care will be censored at Day 28 (when died or discontinued prior to Day 28) or on the date of study withdrawal (when died or discontinued after Day 28).

A table of the corresponding Kaplan-Meier estimates will be presented displaying the number of patients at risk, number of patients censored, number of patients discharged from ICU/Intermediate care, cumulative number of patients discharged from ICU/Intermediate care, Kaplan-Meier estimate, and standard errors of the Kaplan-Meier

estimates. Summary statistics (based on the Kaplan-Meier analysis) for the time to discharge from ICU/Intermediate care will also be included in a separate table.

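### Time to off-ventilator and time to shock-free appear to censor deaths on support at death, so the planned Kaplan-Meier estimates would overstate recovery

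*SAP*

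**What the plan says.** The SAP's rule for the ventilator endpoint, in 8.2.2.2, reads: "Patients that do not have an off ventilator date will be censored at the earliest of Day 28 or date of study withdrawal". On shock, the same section says: "Shock-free days and Time to being shock-free will be analyzed in an identical fashion to the method described above". The planned outputs are Kaplan-Meier plots, a table of estimates, summary statistics from the Kaplan-Meier analysis, and a site-stratified log-rank test with a hazard ratio and 95% confidence interval.

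Protocol 7.3.2 sets the same rule. For the ventilator: "Patients who remain on ventilator will be censored at the earliest of Day 28 or withdrawal from the study for any reason". For shock: "Patients who do not become shock free will be censored at the earliest of Day 28 or withdrawal from the study for any reason".

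None of these sentences names death. Two other places bear on how it is treated:

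- SAP 5.1 ends its list of reasons for study discontinuation with "Protocol Non-Compliance or violation, Death and Other".
- SAP 8.3, on time to ICU discharge, says: "Patients that have not been discharged from the ICU/Intermediate care will be censored at Day 28 (when died or discontinued prior to Day 28"; otherwise they are censored "on the date of study withdrawal (when died or discontinued after Day 28". The second phrase gives a date of study withdrawal to patients who died.

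**The concern.** If death counts as withdrawal, a patient who dies on the ventilator or on vasopressors leaves the risk set on the day of death. Kaplan-Meier then treats that patient as someone who could still have come off support later, at the same rate as those still at risk. Such a patient cannot recover, so one minus the Kaplan-Meier estimate is not the proportion who come off support alive. It is too high, and the median time is too short.

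The SAP handles death differently for closely related endpoints. A patient who dies ventilated on Day 5 counts as ventilated to Day 28 for ventilator-free days but leaves the time-to-off-ventilator analysis on Day 5. At stake is whether readers can take the planned curves and medians as recovery rates in a population where many may die on support.

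**Working it through.** **1. What the censoring rule implies for deaths.** Protocol 7.3.2 censors at withdrawal for any reason. SAP 5.1 counts death as a reason for discontinuation. SAP 8.3 applies the date of study withdrawal to patients who died. Together these make censoring at death the natural reading for the ventilator and shock endpoints.

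**2. How the SAP treats death on related endpoints.**

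- Time to ICU discharge (8.3): deaths before Day 28 are censored at Day 28, so they stay in the risk set.
- Days on RRT (8.2.2.1, exploratory ANOVA): death while on RRT counts as RRT up to Day 28.
- Ventilator-free and shock-free days (8.2.2.2): status at death is carried forward to Day 28.

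**3. Size.** The documents state no event rate, sample size or power for these two endpoints, so there is no figure to reproduce. SAP Section 1 cites SA-AKI mortality of up to 70%, but that is not a rate of death on support. All rates below are assumptions.

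Let λ1 be the daily hazard of coming off support and λ2 the daily hazard of death on support, both constant.

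- True proportion off support alive by Day 28: λ1/(λ1+λ2) × [1 − exp(−28(λ1+λ2))].
- One minus Kaplan-Meier with deaths censored at death: 1 − exp(−28λ1).

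If w come off, d die on support and r = 1 − w − d are still on support at Day 28, then λ1+λ2 = −ln(r)/28 and λ1 = (λ1+λ2) × w/(w+d).

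Example with w = 0.60, d = 0.30, r = 0.10:

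- λ1+λ2 = 2.3026/28 = 0.0822, and λ1 = 0.0822 × 0.60/0.90 = 0.0548.
- One minus Kaplan-Meier = 1 − exp(−28 × 0.0548) = 78.5%, against a true 60%.
- Kaplan-Meier median = ln 2/0.0548 = 12.6 days, against a true 16.9 days.

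Over the assumed range, the first value in each pair has 15% still on support at Day 28 and the second has 5%:

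| Die on support | True recovery | One minus Kaplan-Meier | Excess (points) |
|---|---|---|---|
| 10% | 75%, 85% | 81.2%, 93.1% | 6.2, 8.1 |
| 20% | 65%, 75% | 76.6%, 90.6% | 11.6, 15.6 |
| 30% | 55%, 65% | 70.7%, 87.1% | 15.7, 22.1 |
| 40% | 45%, 55% | 63.4%, 82.3% | 18.4, 27.3 |

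**4. Two arms.** Take λ1 = 0.06 in both arms, with λ2 = 0.01 in one and 0.03 in the other.

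- True recovery: 0.06/0.07 × [1 − exp(−1.96)] = 73.6%, and 0.06/0.09 × [1 − exp(−2.52)] = 61.3%.
- One minus Kaplan-Meier: 1 − exp(−1.68) = 81.4% in both arms, with a cause-specific hazard ratio of 1.

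**5. Effect of each rule.** A simulation (1,000 runs, n = 115, assumed 65% off, 25% dead on support, 10% still on support, no other censoring) gave these mean Day 28 values:

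- True recovery: 65.1%.
- Deaths censored at death: 81.2%.
- Deaths censored at Day 28: 65.1%.
- Stop date at death counted as coming off: 90.1%.

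**The case against.** The strongest objection is that censoring at death is inferred. SAP 8.2.2.2 itself, in the rule for ventilator-free days, names dying and withdrawing as two separate events, as do SAP 8.2.1 and Protocol 7.2. On that usage death is not a withdrawal, deaths on support run to Day 28, and the overstatement disappears. This stands as a caveat. It does not remove the point, because a programmer following SAP 5.1 and 8.3 could reasonably censor at death, and the same sentence is needed under either reading.

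The SAP is also silent on an earlier question. Ventilator start and stop dates come from the eCRF, and the censoring rule covers only patients with no off date. If a stop date entered at death counts as an off date, the censoring rule never applies and death is scored as recovery. This objection stands in full, and a change to the censoring sentence alone would not be enough.

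A reader might infer three stronger things that the documents do not support:

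- That the ventilator and ICU-discharge rules contradict each other. They govern different endpoints and can both be applied, so this is an inconsistency of approach.
- That the planned test is invalid or would show the wrong effect. In step 4 the coming-off hazards are equal, so a hazard ratio of 1 is the correct cause-specific result. Choosing between a cause-specific comparison and one of recovery alive is partly a choice of estimand.
- That a mortality effect would be hidden. SAP 8.2.2.2 compares deaths at Day 28 and Day 90 by a CMH test, and ventilator-free and shock-free days carry forward status at death.

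**Conclusion.** The point holds as an inference about the censoring rule and a bias in descriptive estimates. On the natural reading, the Kaplan-Meier curves, estimates and medians for both endpoints overstate the probability, and understate the time, of coming off support alive. The Day 28 excess is about 6 to 8 points if 10% die on support and 18 to 27 points if 40% do. These figures assume constant hazards and 5% to 15% still on support at Day 28; the documents supply neither those proportions nor a rate of death on support.

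The log-rank test and hazard ratio stay valid as cause-specific comparisons but do not measure recovery alive. SAP Section 4 makes the other secondary endpoints exploratory, so the primary and key secondary conclusions are unaffected. The correction is still worth making because it is cheap and the SAP already uses a suitable rule elsewhere.

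**What to change.** In SAP 8.2.2.2, for both endpoints:

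1. State that patients who die before coming off ventilator or becoming shock-free are censored at Day 28, as for ICU discharge in 8.3. Alternatively, report cumulative incidence with death as a competing event.
2. State that a ventilator or vasopressor/inotrope stop date recorded because of death is not an off-ventilator or shock-free event.
3. Label the hazard ratio for what it measures under the chosen rule.
4. Record the departure from Protocol 7.3.2 in SAP Section 12.

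The cost is a few sentences and some programming; dates of death and of support are already collected. The downside is that, with deaths kept to Day 28, the hazard ratio combines effects on recovery and on death and must be labelled so. If the cause-specific hazard ratio is kept beside the cumulative incidence curves, its label should say that it does not measure coming off support alive.

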## 1 Introduction

Sepsis is a major cause of multiple organ dysfunction and death in the intensive care unit (ICU). Despite modern anti-microbial therapy and intensive care facilities, the mortality rate of sepsis remains high (Martin et al 2003). It is estimated that in the United States alone, sepsis occurs in 750 000 patients per year with a mortality rate of approximately 30% to 50% (CDC 1990; Rangel-Frausto et al 1995; Angus et al 2000; Annane et al 2000). In addition, sepsis is the most common cause of non-cardiac death in the ICU (Parrillo et al 1990). Sepsis is a systemic inflammatory cascade that occurs in the human body in response to an infection with bacteria, or other pathogens (Rackow 1986; Bone et al 1997). Patients with sepsis present with clinical manifestations of systemic inflammation and suspicion or evidence of infection.

Sepsis-associated acute kidney injury (SA-AKI) is a serious condition. Sepsis-associated acute kidney injury results in a mortality rate of up to 70% while patients surviving an episode of acute kidney injury (AKI) are at risk of developing chronic kidney disease (CKD) (Oppert et al 2008; Chawla et al 2011, Vaara et al 2012). Acute kidney injury is thought to be a multi-factorial disease with inflammatory, direct nephrotoxic, and ischemic insults acting simultaneously with other pathogenic responses to rapidly cause functional failure of the kidney (Bonventre and Yang 2011; Wen et al 2011; Gomez et al 2014). In sepsis, the initial host response to an infection, mostly caused by bacteria, becomes amplified and then deregulated, bringing the body into an inflammatory state (Cohen 2002). There are no pharmacological interventions approved for the treatment of SA-AKI. Currently, renal replacement therapy (RRT) is the only supportive treatment option available for AKI (Vincent et al 2006; Oppert et al 2008; Bagshaw et al 2009).

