Sepsis-associated acute kidney injury (SA-AKI) is a serious condition with a mortality rate of up to 70%, while patients surviving an episode of acute kidney injury (AKI) are at risk of developing chronic kidney disease (CKD) ([Oppert et al 2008](#); [Chawla et al 2011](#), [Vaara et al 2012](#)).

As there are no guidelines for the development of drugs for the indication SA-AKI the proposed design of this study was determined to be optimal by a group of leading global experts in AKI and sepsis, and subsequently was discussed (and agreed) with European and United States regulatory agencies.

The study has been set up with an adaptive study design including 2 parts, with dose selection based on an interim analysis after all patients in Part 1 have completed the first 7 days of the study, unless the patient was randomized but died or discontinued prior to completing 7 days. The 3 doses proposed in Part 1 are selected based on a combination of information from previous clinical studies conducted with bovine intestinal alkaline phosphatase (BiAP), and pre-clinical animal models and pharmacokinetic (PK) modeling and simulation in a Phase I healthy volunteer study with recombinant human AP (recAP). Assuming comparable safety profiles, the most optimal dose will be selected at the interim analysis by an independent data monitoring committee (DMC). The primary endpoint, creatinine clearance, was chosen because as a continuous variable it is sensitive for detecting relatively small treatment effect differences of recAP versus placebo, as well as determination of effect size differences between the different dosages. Incidence of dialysis, considered to be a relevant clinical endpoint for Phase 3 pivotal studies, was chosen as the key secondary endpoint. In Part 1 PK samples will be taken to assess the pharmacological properties of recAP in patients, in addition to the information previously derived from the healthy volunteers.

Currently there is no treatment available for SA-AKI; hence, recAP is considered as add-on therapy and with that the use of a placebo arm is fully justified.

Following patients up to a period of 90 days allows for assessing potential disease-modifying characteristics of recAP in kidney function (occurrence or worsening of CKD).

2. Objectives

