Please note that any patients who do not receive any dose of study drug will be excluded from the safety and PP analyses, and therefore do not need to be considered in the [Table 4-1](#). Dose windows were constructed in line with the weight ranges and corresponding pre-calculating volumes displayed in [Table 15-3](#). See [Section 15.3](#) for full justification of these windows.

Statistical Analysis

All statistical tests will be two-sided and performed using a 5% significance level, displaying 95% two-sided confidence intervals (CIs), unless specifically stated otherwise. As the primary efficacy endpoint is analyzed at the interim analysis and at the end of the study, multiplicity will be addressed by using a combination test to combine the results (see [Section 8.1.1](#)). A hierarchical method will be employed to address any multiplicity arising from the analysis of the key secondary endpoint. In other words, the formal analysis of this endpoint will be performed only if a statistically significant result is obtained from the combination test analysis of the primary endpoint. All analyses performed on the other secondary endpoints are for exploratory purposes only; therefore, no further multiplicity adjustment is required.

All analyses will be undertaken using SAS[®] Version 9.2 (SAS Institute, Inc, Cary, North Carolina) or later.

Weight

Body weight (in kg or lb) will be measured or estimated at screening. Weight will be displayed in kg and derived from lb as:

$$Weight[kg] = \frac{Weight[lb]}{2.2046}$$

Temperature

Temperature (in °C or °F) will be measured from Day 1 – Day 28. Temperature will be displayed in °C and derived from °F as:

$$Temperature[°C] = \frac{Temperature[°F] - 32}{1.8}$$

Laboratory Data

For laboratory data that are recorded as values of '<x' and '>x' where x is any numeric value, the numeric part after the '>' and '<' (i.e. x) will be used for summarizing and in graphical presentations. In addition the numeric part will be used in the derivation of the quartile-based subgroup definitions.

In the tables where serum creatinine or CRP data are presented, if a subject has missing baseline central laboratory measured serum creatinine or CRP values, but has available baseline local laboratory measured values then the local laboratory values will be used to

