4.1. Sample Size

A sample size of $n_1 = 30$ patients per treatment group in Part 1 with an additional $n_2 = 85$ patients recruited to each of the optimal recAP dose and placebo treatment groups in Part 2 (for a total sample size of $n = 290$ patients) is planned. Recruitment will continue during the interim analysis, so the total number of patients will exceed 290. Custom programmed simulations were performed using SAS[®] Version 9.2 (SAS Institute, Inc, Cary, North Carolina) to determine power and type I error rate of the chosen sample size and design under a number of different dose response scenarios. Each scenario assumed a standard deviation of 49 mL/min for the primary endpoint (area under the time-corrected endogenous creatinine clearance curve from Day 1 to Day 7 [AUC₁₋₇]) with an assumed response of 60 mL/min for the placebo group, and between 60 mL/min (no treatment effect) and 79 mL/min (strong treatment effect) for the recAP dose groups.

Fifty-thousand simulations were performed to show that the 1-sided type I error rate is 2.4% (and hence is well controlled at the 1-sided 2.5% significance level). The power was defined as the probability of rejecting the null hypothesis (of no difference between treatment groups) when 1 or more recAP dose groups have an effective treatment effect, defined as a response of 69.5 mL/min. This was investigated across 7 scenarios with 10 000 simulations performed for each. In the most realistic scenarios (with strong treatment effects, i.e., responses of 79 mL/min for the medium and high recAP dose groups and a varying response of between 60 mL/min and 79 mL/min for the low-dose group) the chosen design achieved power of between 79% and 86%. This dropped to 66% to 67% for other scenarios where only the high recAP dose group had a strong treatment effect.

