8.2.2. Other Secondary Efficacy Endpoints

Unless stated otherwise all analysis on the other secondary endpoints will compare the optimal recAP with placebo and be based on the ITT Combined Set, i.e. include all patients randomized to those treatment groups during Part 1 and Part 2 of the study. All summary statistics, counts and percentages, and data listings will be based on the ITT Combined Set, displaying results for all four treatment groups and including all patients randomized during Part 1 or Part 2 of the study.

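### Time-to-death Kaplan-Meier output is produced only if a Day 28 or Day 90 mortality test is significant, unlike the SAP's other time-to-event endpoints

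*SAP*

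**What the plan says.** For deaths, SAP 8.2.2.2 always reports counts and percentages at Day 28 and Day 90. It also plans an exploratory test to "compare the number of deaths between the optimal recAP dose and placebo at Day 28 and Day 90 using a Cochran-Mantel-Haenzel (CMH) test", with the statistic and p-value presented. The next step is conditional: "Should either of the CMH tests at Day 28 and Day 90 produce a significant result", time to death over Days 1 to 90 is shown as Kaplan-Meier plots, with a table of estimates and standard errors and a separate summary table. Patients still alive are censored at Day 90 or at study withdrawal, whichever comes first.

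The same SAP gives Kaplan-Meier output without any condition for time off ventilator and time to being shock-free (8.2.2.2), and for time to ICU and hospital discharge (8.3). Cause of death and a listing of all deaths are unconditional (9.1.6). So are the three composites that include death, each with an odds ratio and 95% CI (8.3).

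Protocol 7.3.2 lists deaths over the 90-day study period as an endpoint and attaches no such condition. SAP Section 12 does not record the condition as a change.

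**The concern.** Whether a time-to-event description of death appears in the report depends on the result. Two things follow.

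First, in a trial with no planned power for mortality, the output will often be missing when there is a real difference, in either direction. The report would then have no mortality analysis that accounts for censoring. It would also have no stand-alone mortality estimate with a measure of precision, because the unconditional output consists of counts, percentages and a p-value.

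Second, curves that are shown only after a significant test come from a selected set of trials, and on average they show too large a difference.

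The SAP gives no reason for treating death differently from ventilation, shock or discharge. The exploratory label does not explain it, because those endpoints are also outside formal testing.

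**Working it through.** **Inputs from the documents**
- Patients per arm (SAP 4.1): 30 "patients per treatment group in Part 1 with an additional" 85 "patients recruited to each of the optimal recAP dose and placebo treatment groups in Part 2". That is 30 + 85 = 115 per arm for selected dose against placebo.
- Analysis set (SAP 8.2.2): the comparisons "include all patients randomized to those treatment groups during Part 1 and Part 2 of the study".
- Test level (SAP Section 4, Statistical Analysis): "All statistical tests will be two-sided and performed using a 5% significance level". There is no multiplicity adjustment for these exploratory tests.
- Mortality: no planning rate or effect is given. The only background figures are "a mortality rate of approximately 30% to 50" per cent for sepsis (Protocol Section 1) and "serious condition with a mortality rate of up to 70" per cent for sepsis-associated AKI (SAP Section 1).

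**Assumptions**
- Control Day 28 mortality of 15-60%, with Day 90 mortality of 20-70%.
- A 10-point difference at both days.
- A CMH test without strata, because the SAP names no stratification factor.

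**Step 1. The plan's own figure.** The documents state no power for mortality. The stated primary-endpoint power of 79% to 86% reproduces: simulating the two-part design gave 79.4%, 81.7% and 85.7% with the low dose at 69.5, 60 and 79 mL/min. This supports the reading of the design and the sample sizes.

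**Step 2. One test.** With difference d, pooled standard error SE0 and unpooled SE1, power = Φ[(d − 1.96·SE0)/SE1].
- 30% v 20%: SE0 = √(2 × 0.25 × 0.75/115) = 0.0571; SE1 = √((0.21 + 0.16)/115) = 0.0567. Power = Φ[(0.10 − 0.1119)/0.0567] = Φ(−0.21) = 42%.
- 40% v 30%: SE0 = 0.0629 and SE1 = 0.0626. Power = Φ(−0.37) = 35%.

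The threshold can be seen in counts. With x and y deaths in the two arms, m = x + y and T = 230, the statistic is (x − m/2)²/V, where V = 115²·m(T − m)/[T²(T − 1)]. It must exceed 3.84.
- 35 v 23 deaths (30.4% v 20.0%): 6²/10.89 = 3.31, not significant.
- 35 v 22 deaths: 6.5²/10.77 = 3.92, significant.

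An observed 10.4-point difference would therefore leave the output unproduced.

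**Step 3. The rule as written.** Either test opens the gate, and the two tests share deaths. Day 28 and Day 90 deaths were therefore simulated as nested, with at least 200,000 trials per case.

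| Control Day 28 / Day 90 | Output missing, 10-point benefit | Output missing, 10-point harm |
|---|---|---|
| 15 / 20% | 23% | 47% |
| 20 / 30% | 37% | 51% |
| 25 / 35% | 45% | 54% |
| 30 / 40% | 51% | 56% |
| 40 / 50% | 56% | 56% |
| 50 / 60% | 56% | 56% |
| 60 / 70% | 56% | 51% |

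**Step 4. Sensitivity (benefit).**
- Day 90 control mortality only 5 points above Day 28: 47% missing at 25/30%, about 59% at 40/45%.
- A difference of 5 points at Day 28 and 10 at Day 90: 57-65% missing (control 20/30% to 60/70%).
- CMH stratified by 100 sites: 39-61% missing over the same control range.

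**Step 5. What is shown when the gate opens (control 30/40%).** For a true 10-point difference, the mean Day 90 difference among trials that pass is 14.6 points. For a true 5 points it is 12.9. With no true difference the gate opens in about 8% of trials rather than 5%, because either of two unadjusted tests is enough.

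**The case against.** A reader might infer that survival results are withheld. The documents do not support that. Deaths by arm at both days, the CMH result, causes of death and the listing appear whatever the p-value, so the crude risk difference can always be worked out. The composites with death carry confidence intervals, although they mix death with renal outcomes.

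A reader might also infer that harm could go unseen. The test is two-sided, so significant harm opens the gate too. The DMC outputs in SAP Section 11 include the cause-of-death summary and the deaths listing, independently of this rule.

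A reader who takes one test at a time would put the missing rate at 53% (25% v 15%) or 58% (30% v 20%). That is not the SAP's rule. With those two pairs as Day 28 and Day 90, the either-test gate stays closed in about 47% of trials.

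Three further limits stand:
- The SAP does not say how withdrawals enter the CMH test. Counting them as survivors follows from its default denominator of all patients in the arm, but that is an inference. With few withdrawals the Kaplan-Meier and crude figures would nearly agree.
- Even with the gate open, no log-rank test or hazard ratio is planned for death, so the conditional output is descriptive.
- The mortality rates and the 10-point effect are assumptions.

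None of this supplies a reason for the condition, or for its absence from the other time-to-event endpoints.

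**Conclusion.** The point holds in a limited form. The time-to-death analysis, not mortality reporting as a whole, is conditional on significance. What may be lost is the analysis that censors withdrawals and the only stand-alone mortality estimate with a standard error.

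Missing in about half of trials is a fair summary only for control Day 28 mortality of roughly 25-60% with a 10-point difference at both days. Over all the benefit cases tried, the figure runs from 23% to 65%. It rests on 115 per arm as planned, which continued recruitment during the interim analysis could change, and on assumed mortality. The inflation in Step 5 applies to the set of trials that would show curves; in any single trial the unconditional counts sit beside them.

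The primary and key secondary analyses are not affected. This is an inconsistency in reporting a safety outcome, and it is easily removed.

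**What to change.** In SAP 8.2.2.2, delete the condition and always produce the Day 1 to Day 90 Kaplan-Meier plot, estimates table and summary for time to death, as for the other time-to-event endpoints. Add 95% CIs for the Kaplan-Meier estimates at Day 28 and Day 90. Keep the exploratory label.

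The time origin, censoring rule and table layout are already specified. The cost is one added CI column and output that is already specified.
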